7.1.6 Reproductive Hormone Stopping Criteria

If a subject experiences significant changes from baseline in reproductive hormone(s), the Investigator should determine whether such changes represent clinically significant reproductive abnormalities, potential risks to the subject, whether to discontinue study drug, and appropriate safety follow-up. These changes include but are not limited to significant changes in LH, FSH, or SHBG; significant changes in inhibin B or testicular dysfunction in men; and significant changes in estradiol, prolactin, progesterone, or menstrual cyclicity in women.

Investigators should keep in mind that subjects with CAH can be expected to have abnormal reproductive hormone levels because deficient 21-hydroxylase enzyme activity leads 1) to elevated levels of cortisol precursors that are shunted into reproductive hormone biosynthetic pathways and 2) to low levels of the cortisol that normally provides negative feedback on the HPA axis. Standard-of-care therapy with GC and mineralocorticoid replacement does not necessarily fully normalize adrenal steroid production pathways and signaling systems, including ACTH and CRF levels. Thus, subjects with CAH can be expected to have abnormal plasma concentrations of various androgens and progestogens at baseline. Therapy with an effective CRF receptor antagonist may in fact shift the balance between various intermediates in the steroid biosynthetic pathway. Investigators should inform the Medical Monitor before discontinuing study drug.

7.1.7 Clinically Significant Adverse Event Stopping Criteria

The Investigator should consider study drug discontinuation and appropriate safety follow-up for a subject who experiences a clinically significant AE. When feasible, the Investigator should contact the Medical Monitor to discuss the subject's clinical condition before discontinuing study drug. Clinically significant AEs include but are not limited to study drug-related SAEs ([Section 8.3.2](#)) and study drug-related AESIs ([Section 8.3.8](#)).

7.2 Participant Withdrawal from the Study

Subjects are free to withdraw from the study at any time upon request. If the subject withdraws consent for disclosure of future information, the Sponsor may retain and continue to use any data collected before the withdrawal of consent. The subject may request destruction of any samples taken and not tested, and the Investigator must document this in the site study records.

Subjects will be withdrawn from the study by the Investigator and/or Sponsor for either of the following:

- Pregnancy
- If any clinical AE, laboratory abnormality, or other medical condition or situation occurs such that continued participation in the study would not be in the best interest of the subject

A subject may also be withdrawn from the study by the Investigator and/or Sponsor at any time for other safety, behavioral, compliance, or administrative reasons such as the following:

- Significant protocol deviation or noncompliance with study procedures/restrictions
- If the subject no longer meets eligibility criteria
- Study termination by the Sponsor

Subject withdrawal is expected to be uncommon. If possible, an early termination visit (as shown in the Schedule of Post-Screening Activities in [Section 1.3.3](#)) should be conducted before subject withdrawal. The Investigator must document the date and primary reason for the withdrawal on the appropriate eCRF. Subjects who withdraw prematurely may be replaced at the discretion of the Sponsor to ensure adequate numbers of evaluable subjects.

7.3 Lost to Follow-up

A subject will be considered lost to follow-up if the subject repeatedly fails to attend scheduled visits and study personnel are unable to reach the subject.

The following actions must be taken if a subject fails to attend a required study visit:

- The site must attempt to contact the subject and reschedule the missed visit as soon as possible, counsel the subject on the importance of maintaining the assigned visit schedule, and ascertain whether the subject wishes to and/or should continue in the study.
- Before a subject is deemed lost to follow-up, the Investigator or designee must make every effort to regain contact with the subject, including, where possible, making 3 telephone calls to the subject and, if necessary, sending a certified letter to the subject's last known mailing address (or local equivalent methods). Attempts to contact the subject should be documented in the subject's medical record.
- If the subject continues to be unreachable, the subject will be considered to have withdrawn from the study with a primary reason of lost to follow-up.

8 STUDY ASSESSMENTS AND PROCEDURES

This section describes what study assessments and procedures will be performed and how they will be conducted. The timing of study assessments and procedures is provided in the Schedules of Activities in [Section 1.3](#).

8.1 Efficacy Assessments

8.1.1 Hormone Assessments

All blood samples will be collected at 8 AM (\pm 1 hour) prior to administering their GC dose after an overnight fast (nothing to eat after midnight) unless otherwise specified.

A4, 17-OHP, ACTH, and testosterone will be measured.

Detailed instructions for the collection and handling of biological samples will be provided separately.

8.1.2 Quality of Life Assessments

Quality of life will be measured using the SF-36, the Patient Global Impression of Change (PGIC), and the Clinical Global Impression – Improvement Scale (CGI-I).

8.1.2.1 Short Form 36

The SF-36 ([Ware and Sherbourne 1992](#)) is a widely used, validated, patient-reported survey that assesses subjective health status. The SF-36 consists of 36 items and the following 8 health domains: physical functioning, role-physical (limitations in usual role activities because of physical health problems), bodily pain, general health perceptions, vitality, social functioning, role-emotional (limitations in usual role activities because of emotional problems), and mental health. Domain scores range from 0 to 100, with higher scores corresponding to better subjective health status. The survey provides summary scores for physical health and mental health.

8.1.2.2 Patient Global Impression of Change

The PGIC ([Guy 1976](#)) is a 1-question survey that asks subjects to evaluate whether there has been an improvement in overall subjective health status. Subjects select a response on a 7-point Likert scale.

8.1.2.3 Clinical Global Impression – Improvement Scale

The CGI-I ([Guy 1976](#)) is a 1-question survey that requires the clinician to assess how much a patient's illness has improved or worsened relative to a baseline state. Clinicians select a response on a 7-point Likert scale.

8.1.3 Metabolic Assessments

A lipid panel (total cholesterol, low-density lipoprotein [LDL], high-density lipoprotein [HDL], and triglycerides) and hemoglobin A1c (HbA1c), fasting glucose, and fasting insulin will be assessed as part of clinical laboratory (see [Section 13.3](#)). Homeostatic model assessment of insulin resistance (HOMA-IR) will be calculated from fasting glucose and fasting insulin. Blood pressure (systolic and diastolic) will be assessed. Body weight, BMI, and waist circumference will be assessed as described in [Section 8.2.3](#).

8.1.4 Hyperandrogenic Symptoms

8.1.4.1 Acne

Acne severity will be evaluated using an IGA score ([FDA 2018](#)). Qualified medical professionals will assess the IGA score.

Information regarding any concomitant medications for acne, including topical treatments, should be solicited from subjects.

8.1.4.2 Hirsutism

Hirsutism will be evaluated in female subjects using a mFG score ([Yildiz 2010; Martin 2018](#)). Qualified medical professionals will assess the mFG score. The mFG scores each of 9 body areas on a scale of 0 (no hair) to 4 (hairiness typical of a man), with the sum of the separate scores providing a hormonal hirsutism score.

Information regarding any concomitant medications or depilatory methods for hirsutism should be solicited from subjects.

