8.2.6.2 Hospital Anxiety and Depression Scale

Subject anxiety and depression will be monitored during the study using the HADS, assessed at Weeks 6, 18, 30, 58, 70, and 76 ([Zigmond and Snaith 1983](#)). The HADS is a widely used subject-reported instrument that focuses on subjective disturbances of mood rather than physical signs. The scale consists of 14 items, 7 items each for anxiety and depression. Each item is rated on a 4-point scale based on the frequency of symptoms over the preceding week and ranging from 0 (not at all) to 3 (very often).

Refer to [Section 7.1.4](#) for depression and/or anxiety individual treatment-stopping criteria.

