9.4.4.4 Patient- and Clinician-Reported Outcomes Endpoints

Changes in SF-36 total score, IGA acne score, and mFG hirsutism score will be analyzed using a repeated measure mixed effects model with treatment (two covariates: randomized and group at Week 76) and visit as fixed effects, subject as a random effect, and the baseline score as a covariate if >2 timepoints are assessed. If only the baseline timepoint and a single post-baseline timepoint are assessed for the endpoint, an ANCOVA model with the baseline score as a covariate will be used with only a single treatment covariate (randomized treatment). There will be no imputation of missing data.

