### 9.3.17 HADS Total Score

The scale consists of 14 items, 7 items each for anxiety and depression. The anxiety score is the sum of the odd-numbered items (questions 1, 3, 5, 7, 9, 11, 13), and the depression score is the sum of the even-numbered items (questions 2, 4, 6, 8, 10, 12, 14).

Each item is rated on a 4-point scale based on the frequency of symptoms over the preceding week and ranging from 0 (not at all) to 3 (very often). The sub-scores are the sum of individual item scores within each subcategory (anxiety or depression) and ranges from 0 to 21, with higher scores corresponding to higher levels of anxiety or depression. The total score of the individual item scores and ranges from 0 to 42, with higher scores corresponding to higher levels of anxiety or depression.

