#### **9.3.19 Modified Ferriman-Gallwey Total Score**

The mFG scores each of 9 body areas on a scale of 0 (no hair) to 4 (hairiness typical of a man), with the sum of the separate scores providing a hormonal hirsutism score.

The total score is the sum of the individual item scores and ranges from 0 to 36, with higher scores corresponding to body hair patterns more typical of a man.

A subject with hirsutism at baseline is defined as an mFG score of 8 or more.

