### **10.2.2 Handling of Questionnaire Data**

A total score for questionnaires will be calculated so long as  $> 50\%$  of the items are non-missing. Otherwise, the total score will be set to missing.

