Since the change from baseline in IGA or mFG may have sparse values may have sparse values (i.e., < 5 distinctive values with counts  $\geq 5$ ), the change from baseline values will be further classified in fewer ordered categories (i.e., improvement, no change, worsening) prior to analysis.

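### The SAP lets a HADS total (and, on the likeliest reading, an mFG total) be formed with just over half the items answered but defines it as a plain sum, so an incomplete form reads low

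*Protocol*

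**What the plan says.** **Scales.** Protocol 8.1.4.2 scores nine areas from 0 to 4, "with the sum of the separate scores providing a hormonal hirsutism score". SAP 9.3.19 repeats this ("The total score is the sum of the individual item scores and ranges from 0 to 36") and defines hirsutism at baseline as a score of 8 or more. For HADS, Protocol 8.2.6.2 states "The scale consists of 14 items, 7 items each for anxiety and depression", each rated 0 to 3. SAP 9.3.17 adds "The sub-scores are the sum of individual item scores within each subcategory", with a range of 0 to 21 per sub-score and 0 to 42 in total. On both scales higher is worse.

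**Missing items.** SAP 10.2.2 reads: "A total score for questionnaires will be calculated so long as" more than half of the items are present; otherwise the total is missing. SAP 10.2 says that missing data will be imputed as set out in its subsections, but 10.2.2 contains no method. On the analysis of SF-36, acne and mFG changes, Protocol 9.4.4.4 says "There will be no imputation of missing data".

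**Use.** SAP 14.5.1 summarizes the HADS total and its change from baseline. mFG change at Week 76 is Exploratory Efficacy Analysis 3.9. Under SAP 13.5.7, if change values are sparse they "will be further classified in fewer ordered categories (i.e., improvement, no change, worsening) prior to analysis".

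**The concern.** A threshold that permits incomplete forms needs a formula that allows for the gaps. The only formula given is a sum. Summing the answered items gives a blank the value 0, which on these scales means no hair or no symptom. The score can then only stay equal or fall.

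The effect on change from baseline depends on which visit is incomplete:

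- **Incomplete follow-up form:** a spurious fall, read as improvement. SAP 13.5.7 judges Week 76 against baseline, and every subject is moved to 200 mg at Week 30, so no concurrent placebo arm offsets the fall. If change is collapsed to three categories, one unscored area with a non-zero true score can turn no change into improvement.
- **Incomplete baseline form:** a spurious rise, read as worsening. For mFG it can also take a woman below 8 and out of the hirsutism analysis.

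The threshold also applies to the whole HADS, so it does not ensure that either subscale is adequately answered.

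**Working it through.** **Inputs.** mFG: 9 areas, maximum 4 each (Protocol 8.1.4.2, SAP 9.3.19). HADS: 14 items in two sets of 7, maximum 3 each (Protocol 8.2.6.2, SAP 9.3.17). Threshold: more than 50% of items present (SAP 10.2.2). Hirsutism cut: 8 (SAP 9.3.19).

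**The plan's own ranges.** 9 × 4 = 36; 14 × 3 = 42; 7 × 3 = 21. All three match, and they confirm that the HADS total is a sum, which SAP 9.3.17 leaves incompletely worded.

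**Fewest items allowed.**

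- mFG: half of 9 is 4.5, so at least 5 areas; up to 4 missing, 4/9 = 44.4%.
- HADS: half of 14 is 7, so at least 8 items; up to 6 missing, 6/14 = 42.9%.

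**Plain sum when the missing items are average ones** (true score × items present / items in scale):

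| Scale | True score | One missing | Most missing allowed |
|---|---|---|---|
| mFG | 18 | 18 × 8/9 = 16 | 18 × 5/9 = 10 |
| mFG | 14 | 14 × 8/9 = 12.4 | 14 × 5/9 = 7.8 |
| mFG | 8 | 8 × 8/9 = 7.1 | 8 × 5/9 = 4.4 |
| HADS | 21 | 21 × 13/14 = 19.5 | 21 × 8/14 = 12 |

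An unchanged mFG of 18, complete at baseline and missing four areas at Week 76, therefore gives a change of 10 − 18 = −8. With the visits reversed it gives +8.

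**The cut of 8.** With four average areas missing at baseline, true scores from 8 to 14 read 4.4 to 7.8, all below the cut. With one average area missing, a true 8 falls below (7.1) but a true 9 does not (9 × 8/9 = 8.0). At the extreme, where the four unscored areas each rate 4, a true 7 + 16 = 23 reads 7.

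**Whole-scale threshold on HADS.** Seven anxiety items plus one depression item is 8/14 = 57%, so a total is calculated with 6 of 7 depression items blank. Depression then contributes at most 3 of its 21 points.

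**Pro-rating** (mean of answered items × number of items):

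- mFG: five areas summing to 10 give 10/5 × 9 = 18.
- HADS: four answered items summing to 6 in each subscale give 6/4 × 7 = 10.5 each, total 21.

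Both restore the true value when missing items are average. They do not when the missing item is unusual. Take a true mFG of 18 with one area unscored:

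- That area rates 3: plain sum 15; pro-rated 15 × 9/8 = 16.9, which rounds to 17.
- That area rates 0: plain sum 18; pro-rated 18 × 9/8 = 20.25, which rounds to 20.

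Pro-rating removes the systematic downward error but can still misclassify a small change in either direction.

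**The case against.** **The SAP never says to score a blank as 0.** Section 10.2.2 says when a total is calculated, not how. That is correct; zero-scoring follows from combining it with the sums in 9.3.17 and 9.3.19. But if a blank made the sum missing, the 50% threshold would do nothing. The threshold only has an effect if incomplete forms are summed, and no other formula is offered.

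**mFG may fall outside the rule.** It is rated by a medical professional, and 10.2.2 is headed as questionnaire data. This stands as a caveat. Against it, SF-36 scores arrive already computed (SAP 9.3.18), and PGIC and CGI-I are single questions. HADS and mFG are the multi-item totals that the SAP itself defines, both under Total Score headings. If 10.2.2 does not reach mFG, no item-level rule does.

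**A reader might infer that imputation is ruled out for both scales.** The documents do not support that. Protocol 9.4.4.4 concerns the analysis of SF-36, acne and mFG changes and does not discuss items within a form. For HADS there is only silence.

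**A reader might infer that depression or anxiety would go undetected.** The documents do not support that either. Stopping rests on Investigator-assessed CTCAE Grade 3 or higher (Protocol 7.1.4), and special-interest reporting on Grade 2 or higher (Protocol 8.3.8). Neither uses the HADS total, and Protocol 9.4.6.7 lists the HADS data.

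**Pro-rating is imperfect and gives non-integers for an endpoint modelled as ordinal.** This stands. It is why the fix includes rounding and a complete-form analysis.

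**Conclusion.** The point holds for the score: followed as written, an incomplete HADS form, or an mFG form if the rule reaches it, reads equal to or below the true value. It is tempting to say that the error always favours tildacerfont. It does not, because change from baseline can err either way depending on the incomplete visit.

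The largest permitted understatement with average missing items is 42.9% for HADS (21 reads 12) and 44.4% for mFG (18 reads 10). These are worst cases; one missing item costs 1/14 or 1/9 of the score on average. The documents give no rate of incomplete forms, so the effect in practice is unknown.

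The stakes are limited. HADS is a descriptive safety summary, and mFG (3.9) is exploratory and outside alpha control (SAP 10.5). The primary A4 analysis and the secondary A4 and 17-OHP analyses are untouched. The conclusion assumes that answered items are summed as defined and, for mFG, that 10.2.2 applies. Correction is still warranted because a stated threshold and a stated formula together give a wrong score, and the repair is cheap.

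**What to change.** Amend SAP 9.3.17, 9.3.19 and 10.2.2 as follows.

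- **HADS:** score each subscale as the mean of its answered items × 7 if more than 50% of its 7 items are answered (at least 4); otherwise set it to missing. The total is the sum of the two subscales, and is missing if either is missing.
- **mFG:** state that the rule applies. Score as the mean of the scored areas × 9, rounded to the nearest integer, if more than 50% of the 9 areas are scored (at least 5); otherwise set it to missing.
- **mFG sensitivity:** repeat the improvement / no change / worsening analysis in subjects whose mFG forms are complete.

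The cost is a few sentences of SAP text, a small programming change and one additional exploratory table, with no new data. There are two downsides. A few HADS totals that would now be calculated become missing. Pro-rating also assumes that unscored areas or items resemble the scored ones, which the complete-form analysis lets a reader check for mFG.

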8.1.4.3 Testicular Adrenal Rest Tumors

TARTs are a common complication of CAH caused by ACTH-driven overstimulation of aberrant adrenal cells within the testes ([Olpin and Witt 2014](#)) and may result in pain, discomfort, impaired spermatogenesis, and infertility ([Chihaoui 2016; Claahsen-van der Grinten 2014; Delfino 2012](#)). Complete scrotal ultrasounds will be obtained for male subjects using a real-time scanner to detect and to evaluate the size and number of TARTs. Standard images should be obtained in the longitudinal and transverse planes. Each potential TART lesion will be measured in 3 planes to allow for calculation of TART volume. Detailed instructions for performing the scrotal ultrasound will be provided separately.

The initial scrotal ultrasound may be scheduled for any time up to the Week 4 visit and will be considered the baseline measurement for the TART endpoint. Only subjects with a TART at baseline will be followed for TART changes. Scrotal ultrasounds will be read by a central radiologist blinded to treatment assignment and to the study timepoints at which ultrasounds were taken.

8.1.4.4 Menstrual Cyclicity

Female subjects will record menstrual information in their electronic study diaries, including the start and stop dates of menses.

8.2 Safety Assessments

Safety assessments will include monitoring and recording all AEs (including SAEs, AEs leading to discontinuation/withdrawal, and AESIs), physical examination, vital signs assessment, ECGs, clinical laboratory, monitoring for suicide risk, and depression/anxiety. AE procedures are described in [Section 8.3](#).

8.2.1 Physical Examination

A full physical examination should include assessments of the cardiovascular, respiratory, GI, neurological, and musculoskeletal systems; head, eyes, ears, neck, and throat (HEENT); thyroid; skin; and extremities. The full physical examination may exclude rectal, genitourinary, and breast exams.

An abbreviated physical examination should include the following components: cardiovascular, respiratory, abdomen, musculoskeletal, HEENT, and skin.

Investigators should pay special attention to clinical signs related to previous serious illnesses.

A full physical examination will be performed during the Screening Visit and at Day 1, Week 18, and Week 76. If the physical exam is performed at the subject's home, the qualified medical professional will report any changes to the subject's health to the site to determine whether further evaluation is needed via an unscheduled visit.

8.2.2 Vital Signs

Vital signs consist of systolic and diastolic blood pressure, pulse rate, respiration rate, and body temperature. The subject should rest for at least 5 minutes before vital signs measurement without speaking or using a cellphone. The subject should ideally have an empty bladder. Vital signs will be measured as specified in the Schedules of Activities and as clinically indicated.

Blood pressure should be measured with an appropriately sized cuff on a bare arm just above the bend of the elbow. An appropriately sized cuff has the inflatable portion covering approximately 40% of the arm's circumference and the width of the cuff covering approximately 80% of the area from the elbow to the shoulder. The subject should be sitting in an upright position with feet flat on the floor and the measurement arm supported at heart level.

8.2.3 Body Weight, Height, BMI, and Waist Circumference

Body weight will be measured at every visit using a calibrated balance. The weight should be placed on a hard, flat surface and checked for zero balance before each measurement. The subject should stand unassisted, in the center of the platform, and be asked to look straight ahead, standing relaxed but still.

Height needs to be recorded at screening only.

BMI will be calculated for every visit using height and weight measurements.

Waist circumference will be measured using an appropriate tape measure placed horizontally just above the hip bones at the level of the belly button, placed snugly but not compressing the skin, and after the subject breathes out.

8.2.4 Electrocardiogram

A 12-lead ECG will be obtained using an ECG machine that automatically calculates the heart rate, QRS, QT, and QTc intervals, preferably using Fridericia's formula. Any ECG measurement assessed by the Investigator as a clinically significant abnormality should be recorded in the AE section of the eCRF and monitored until resolution.

Refer to [Section 7.1.2](#) for QT individual treatment-stopping criteria and any additional ECGs that may be necessary.

